#### 3.7 Sample Size:

By using NCSS PASS v.11 repeated measure analyses of variance (RMANOVA), at 80% power, and 95% confidence interval., RMANOVA of STAI Anxiety score for interventional group at Pre-Intervention means 42.01 (SD=12.96), Post intervention means 37.27 (SD=13.47) and 2 weeks post intervention means 38.40 (SD=10.55) [11], The sample size calculated was 30 samples per group. After adjusting error in non-response of data collection 50 samples were drawn from each group. Total 100 caregivers along with their children was recruit in this study.

#### 3.8 Sampling Technique:

Samples were randomly drawn by using block randomization list. This allocation was based on computer generated random allocation with randomly selected size of block i.e. number of patients on a given day. The participation of each parent in each session was based on the given generated numbers. For example, if on a given day block of parents was recommended by the consultant to the researcher then based on generated block random number; parents were allocated to either intervention arm or control arm. The same procedure was repeated on other day until the sample size in each group was completed. This sampling technique was referred as stratified random sampling.

#### 3.9 Data Collection Procedure:

- Approval: Being a part of academic research, approvals were taken from scientific committee, institutional review board (IRB) and Board of Advanced Studies and Research (BASR) of Dow University of Health sciences, Karachi. Then ethical review committee of Research Department, Indus hospital Karachi was obtained where the study participants were approached.
- 2. **Multimedia Room arrangement**: A room was arranged for multimedia chemotherapy education.
- 3. **Approach to target population**: The target population was approached through Pediatrics oncology registration counter. A help was also taken from the primary adviser to acknowledge each newly advised chemotherapy children along with their parents to Multimedia education room.
- 4. **Parent selection:** In the multimedia room, consent was taken from the parents and they were selected according to the above-mentioned inclusion and exclusion criteria.
- 5. **Randomization:** The parents were allocated to Intervention group and Control group per the generated random number as mentioned in sampling technique defined in section 3.8.
- 6. Socio-demographic and others information: The socio-demographics and others information were collected as given in Annexure -1.
- Pre-Intervention Anxiety, Depression and stress: Parent's anxiety, depression and stress levels were assessed by using DASS-21 (Urdu version) as mentioned in Annexure –II.
- 8. **Post-intervention Anxiety, Depression and stress:** After two weeks the anxiety, depression and stress levels were again assessed by using DASS-21 after multimedia education of "Pre-intervention anxiety and depression" identification. The data were collected during next appointment/mail/Telephonic follow up. The main objective of post intervention was to measure the mean difference of DASS score against Pre-intervention.

- 9. 2-week Post-Intervention Anxiety, Depression and stress: The parent anxiety, depression and stress were again assessed after two weeks of 'post intervention anxiety depression" identification. The technique of data collection was same as mentioned under Pre and post intervention. The main objective of two-week post intervention was to measure the mean difference DASS score against Post-intervention
- 10. Anxiety, depression and stress mean difference: Finally, mean differences in the anxiety and depression level of parents in both Intervention Group and Control group were measured.
- 11. **Recruitment**: The parents were recruited in the study from September 2018 to November 2018 and follow up were continued from October 2018 to December 2018. After the completion of follow up to 5th December 2018 the trail was ended due to the completion of target sample sized (N=100) of parents and follow up schedule.

#### 3.10 Interventions:

After an intensive literature review [11, 18, 24-29, 37-39, 42, 44, 46, 52, 54, 55, 58, 61, 62] following intervention strategy was develop in consultation with expert Pediatric Oncologist detail as mentioned below.

#### 3.10.1 To Intervention group:

#### **Before chemotherapy:**

- Multimedia Education: The Intervention group received 60 minutes of PowerPoint multimedia education in Urdu language about chemotherapy, its side effect and nutritional guide. The copy of PowerPoint presentation is given in Annexure –III. It was ensured that well explained and comfortable friendly environment was provided to the parents.
- 2. Booklet providence: A booklet "Chemotherapy and you" in Urdu translation were provided to the parents focusing on the detailed information about chemotherapy and its side effects management. The copy of the booklet is enclosed in Annexure –VI.

# After chemotherapy:

Follow up were done, during follow up side effect appear in their child were determined and the parents were re-educated as per their appearance. There were 18 side effect of chemotherapy in booklet and it was not necessary that all would appear, e.g. example after chemotherapy the child may develop vomiting and diarrhea, but other 16 side effect may remain silent or appear later.

#### 3. Tele-Nursing follow-up:

- **3.1** The parents were provided opportunity to call from 9:00 a.m. to 5:00 p.m., in any week day to ask question related to chemotherapy and its side effect management according to booklet. The education was again provided according to the booklet. If any information asked by parents was not related to the booklet, they were referred to their primary consultant.
- 3.2 Each parent was called by the researcher on weekly basis according to following schedule, day of education (day 0) to 7th, 14th, 21st and 28th day. The content of telephonic conversation majorly focused on (i) list of problem related to chemotherapy side effect and (ii) Management techniques according to the booklet. The approximate duration of call was 15 minutes depending upon the problems identified by the parents.

## 3.10.2 To control Group:

## **Before chemotherapy:**

They were recruited in the study and were informed about the day of data collection for post-analysis.

# After Chemotherapy:

Control group followed routine care. During routine care parent verbally educated by the physician and nurses about Chemotherapy and Side effect Management.

#### 3.11Pilot Study:

#### Content Validity of Booklet "Chemotherapy and you"

The pilot study was conducted to ensure the 'content validity' of educational material "*Chemotherapy and You*', as it was adopted through international Guideline of NIH: National Cancer Institute, so that applicability of educational guideline at Department of Pediatric Oncology at Indus hospital, Karachi need to be ensured. Though, minor changes were determined in the education materials during pilot study which were later incorporated under the supervision of expert reviewers in educational material according to educational need of parents and study setting.

# Training of Principal Investigator for Multimedia education and telephonic Follow up:

During Pilot Study, researcher was also observed and guided by the most senior expert educationist already working in education department from 'Department of Pediatric Oncology Indus hospital Karachi", on how to educate the Parents on multimedia education and Telephonic Follow up. After ensured that, researcher is capable to educate Parents, preceded to final study. It was also ensure that no additional information other than booklet "Chemotherapy and you" will be given. If parents will asked any question other than booklet, will be refer to primary consultant.

#### **Reliability of DASS-21 Scale:**

Although DASS-21 Scale is a reliable tool and has an evidence of its usage in Pakistani context. But in order to ensure its local applicability, total 10 samples (10% of sample size of original study) were taken and it was found a 88.7% reliable. From control group, it shows 92.5% reliability and from intervention group it shows 67.4% reliability.

#### 3.12Ethical Consideration:

The research study got approvals from the scientific and ethical bodies as defined in section 3.9. Furthermore, signed consent was obtained from the selected participants after briefing the information about study. They were told that their relevant personal informed like names of child and parents, their phone number would only be used for telephonic follow up with parents and would be kept confidential within investigators of the study.

#### 3.13 Study Variables

# 3.13.1 Dependent Variable:

Depression (D) anxiety (A) and stress (S) were outcome variables. [63]. They were identified by using DASS-21 Scale. The use of DASS-21 scale was evident in different research studies from Pakistan [62, 64-67]. There were 21 questions in this scale equally divided into three parts having seven questions for Depression, Anxiety and stress respectively. Each question had four level of measurement 0, 1, 2 and 3, represent past week experiences. 0 means not applicable to person, 1 means applicable to some degree or sometime, 2 means applicable to considerable degree or good part of time, 3 means applicable to person very much or most of the time. Each question was separated for Stress(s), Anxiety (a) and Depression (d). The questions focusing the concept (1) (s) hard to wind down, (2)(a) dryness of mouth, (3)(d) experience of positive feeling, (4)(a) breathing difficulty, (5)(d) difficulty in initiation of work, (6)(s) overreaction according to situation, (7)(a) experience of trembling in hand, (8)(s) use of excessive nervous energy, (9)(a) worriedness about panic situation, (10)(d)noting to look forward, (11)(s) getting agitated, (12)(s) difficulty in relaxation, (13)(d)feeling of downhearted and blue, (14)(s) lack of tolerance, (15)(a) feeling of panic, (16)(d)lack of enthusiasm, (17)(d)lack of worthiness as a person, (18)(s) feeling of somewhat sensitive, (19)(a) palpitation and increase of heart beat, (20)(a) feeling of scary and (21)(d) feeling of meaningless life. The cut-off scoring for (1) Depression was Normal (0-9), Mild (10-13), Moderate (14-20), severe (21-27) and extreme Severe (28+), (2) Anxiety was Normal (0-7), Mild (8-9), Moderate (10-14), severe (15-19) and extreme Severe (20+)and (3) Stress was Normal (0-14), Mild (15-18), Moderate (19-25), severe (26-33) and extreme Severe (34+). For further categorical analysis, the depression, anxiety and stress were dichotomized into "No" and "Yes" where "Yes" category was generated while combining the statuses of "mild", "moderate", "severe" and "extremely severe". The Scores on DASS-21 scale was multiplied by 2 to get the final score.

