#### Result

Total 63.4% (n=48) children were under 12 years of age and 64.9% (n=50) children were male. Majority of the parents were non-residence of Karachi, labor and low education and income. 66.2% (n=51) children diagnosed with leukemia, 63.6% (n=49) children had no pain. At the baseline, depression was found in 84.4% (n=56) parents while 67.5% (n=52) parents were anxious and 55.8%(n=43) parents had stress, After the MBT intervention, significant reductions were observed in depression and stress (P-Value <0.05) of the parents in MBT group. A sharp decline was observed just after one week while at final stage intervention group showed higher decrease in depression and stress while anxiety was observed insignificantly different in both groups,

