#### Aim of the study:

The aim of this study is to determine the effects of nurse led chemotherapy education on parent's anxiety and depression, as parents have the key role in caring their children cancer. This study helped to examine the effects of psycho-education about chemotherapy and its side effect management on parent's anxiety, depression and stress at Department of Pediatric Oncology at Indus hospital, Karachi Pakistan.

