#### 1.4 Objectives

To measure the effect of nurse-led multimedia education, booklet providence and telephonic follow up about chemotherapy and side effects management on parent's anxiety, depression and stress of children receiving chemotherapy for the first time

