# 5.5 Conclusion:

There is a positive effect of nurse-led multimedia education, booklet providence and telephonic follow up about chemotherapy and side effects management on parent's depression and stress of children receiving chemotherapy showing in this study for the first time in Pakistan. For anxiety reduction, other strategies should also be incorporated.

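### Depression, anxiety and stress are each tested at 0.05 with no primary outcome and no multiplicity rule; under Holm the depression and stress claims stand, at 0.036 rather than 0.012

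*Combined protocol and SAP*

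**What the plan says.** **Outcomes.** Section 3.13.1: "Depression (D) anxiety (A) and stress (S) were outcome variables". The objective in section 1.4 concerns "side effects management on parent's anxiety, depression and stress of children receiving chemotherapy for the first time", and the research question in section 1.5 lists the same three. No section ranks them.

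**Analysis.** Section 3.14 describes a one-way repeated-measures ANOVA of DASS-21 scores over time, with post hoc comparisons of days 0, 14 and 28. It contains no between-arm test, alpha split, testing order or adjustment.

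**Threshold.** The abstract reports that "significant reductions were observed in depression and stress (P-Value <0.05) of the parents in MBT group". Table 4 gives between-group p-values of 0.012 (depression), 0.172 (anxiety) and 0.012 (stress).

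**Sizing.** Section 3.7 works "at 80% power, and 95% confidence interval" from "RMANOVA of STAI Anxiety score for interventional group at Pre-Intervention means 42.01 (SD=12.96" and two later means for the same single group, and arrives at 30 per group. The scale is the STAI, not the DASS-21.

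**Conclusions.** Section 5.5 opens "There is a positive effect of nurse-led multimedia education" and limits the effect to depression and stress; for anxiety it asks for further strategies. Section 5.6 is limited in the same way. Four other places in Chapter 5 are not: the discussion of MBT as a nursing intervention (twice), section 5.3 and section 5.10 all list anxiety among the things the intervention reduces.

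**The concern.** With three outcomes of equal rank, three separate tests at 0.05 and no rule for what counts as success, a positive finding could have been reported from any one of them. The nominal 5% then applies to each test but not to the set of claims. The claims made are those for the two tests that passed.

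The same gap leaves the document inconsistent about anxiety. It is non-significant between arms in the abstract, section 4.3.3 and section 5.2, yet it is counted as a benefit in parts of Chapter 5, and no decision rule says which statement governs. Section 5.3 also claims good power by reference to the sample size from section 3.7, and that calculation does not address any of the three between-arm tests.

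**Working it through.** **1. The plan's own figure: 30 per group (section 3.7).** Inputs: STAI means 42.01, 37.27 and 38.40; SDs 12.96, 13.47 and 10.55; power 80%; alpha 0.05 (taken as two-sided in the formulas where sidedness matters; the section does not say).
- Pooled variance = (12.96² + 13.47² + 10.55²)/3 = 153.57, so SD = 12.39.
- Squared deviations of the three means from 39.23 sum to 12.26.
- For a time effect pooled over two arms of n, the noncentrality is 2n × 12.26 / [153.57 × (1 − ρ)], where ρ is the within-person correlation. The section gives no ρ.
- Required n per group is 62, 44, 31 and 19 at ρ = 0, 0.3, 0.5 and 0.7. The stated 30 is approached at an assumed ρ of 0.5, for a *time* effect.
- For the arm-by-time interaction, with the same inputs and a flat control arm assumed, the requirement is 122 per group at ρ = 0.5 and 50 at ρ = 0.8.

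So the inputs describe change over time in one arm on another scale. They do not provide power for a between-arm DASS-21 comparison on any outcome.

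**2. Familywise error for three tests at 0.05.**
- Independent tests: 1 − 0.95³ = 1 − 0.8574 = 0.143. The upper bound is 3 × 0.05 = 0.15.
- Correlated tests: three standard normals with common correlation r, two-sided, 1 million draws. The documents give no r, so these values are assumed.

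| r | At least one false positive |
|---|---|
| 0 | 14.3% |
| 0.5 | 12.5% |
| 0.6 | 11.8% |
| 0.8 | 9.8% |

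**3. Adjusting the printed between-group p-values (Table 4).** Holm: sort as 0.012, 0.012, 0.172; multiply by 3, 2, 1; keep the running maximum.
- 3 × 0.012 = 0.036
- max(0.036, 2 × 0.012) = 0.036
- max(0.036, 1 × 0.172) = 0.172

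| Outcome | Raw | Holm | Bonferroni |
|---|---|---|---|
| Depression | 0.012 | 0.036 | 0.036 |
| Stress | 0.012 | 0.036 | 0.036 |
| Anxiety | 0.172 | 0.172 | 0.516 |

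Rounding does not matter: a raw value as high as 0.0125 gives 0.0375.

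**4. What the printed p-values appear to test.** Section 3.14 does not say, so I rebuilt a group effect averaged over all three visits from Table 2. For anxiety the arm differences (intervention minus control) are +1.18, −2.41 and −2.52, mean −1.25. At an assumed within-person correlation of 0.5, the variance of a parent's three-visit average is 11.67 (intervention) and 18.91 (control), pooled 15.05. Then SE = √[15.05 × (1/41 + 1/36)] = 0.886, t = −1.41 on 75 df, p = 0.162. At correlations of 0.5 to 0.6 the reconstruction gives 0.011 to 0.015 for depression, 0.162 to 0.181 for anxiety and 0.009 to 0.012 for stress, close to the printed 0.012, 0.172 and 0.012. The printed tests therefore look like averages that include the pre-intervention visit. At day 28 alone, Welch tests from Table 2 give −3.48 (p = 0.0005) for depression, −2.52 (p = 0.0007) for anxiety and −3.95 (p = 0.0002) for stress. These are post hoc comparisons in the 77 of 100 parents analysed. They do not replace the reported tests, but they show that the adjusted values depend on a test the plan has yet to specify.

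**5. Statements on anxiety, side by side.** Not significant between arms: abstract, section 4.3.3 with Table 4, the opening of Chapter 5, section 5.2. Credited as reduced: the discussion of MBT as a nursing intervention, which cites a fall from 11.35 to 2.98 (the Total column of Table 2, both arms pooled) and closes by naming all three outcomes; section 5.3; section 5.10. A fall pooled over both arms cannot be attributed to the intervention.

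**The case against.** The strongest reply is that nothing is hidden and nothing changes. All three tests are reported, section 5.5 makes outcome-specific claims, and 0.012 is below 0.05/3 = 0.0167, so the same two claims would follow from a rule that holds familywise error at 5%. The 14.3% figure also needs independence, which is implausible for three subscales of one questionnaire answered by the same parents. All of this stands, and it limits the point to a missing rule and overstated strength of evidence. It does not supply the rule, and even at a correlation of 0.8 the error rate is nearly twice the nominal 5%.

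It can also be said that Holm chosen now is chosen with the p-values in view. That is true and should be disclosed. Naming one primary outcome now would be worse, whereas Holm respects the equal ranking in sections 1.4 and 3.13.1.

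Three stronger readings are tempting, and the documents do not support them:
- *That the anxiety result is concealed.* It is stated in the abstract, section 4.3.3, Table 4, the opening of Chapter 5 and section 5.2.
- *That stress was added to obtain a positive result.* One sentence of the aim speaks of "effects of nurse led chemotherapy education on parent's anxiety and depression" without stress, but the next sentence of that section, the objective and the research question all include it.
- *That the trial failed on the outcome it was sized for.* Section 3.7 used STAI change over time in one arm; 0.172 is a between-group DASS-21 test. The time effect for anxiety, the kind of effect for which section 3.7 gives inputs, was below 0.0001.

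**Conclusion.** The point holds as a missing decision rule. Three co-equal outcomes tested at 0.05 carry a familywise error of about 10% to 14% (9.8% at an assumed correlation of 0.8, 14.3% under independence) in place of 5%. The depression and stress claims in the abstract and section 5.5 survive Holm and Bonferroni at 0.036 each, so they stand with weaker evidence than the printed 0.012. This rests on the Table 4 values being the between-arm tests intended; section 3.14 does not define them.

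The anxiety value of 0.172 means not significant on the reported test. It is not evidence of no effect, nor does it show that a de facto primary outcome was missed. What is wrong on anxiety is the set of Chapter 5 statements that claim a reduction from the intervention despite that result.

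**What to change.** - **Section 3.14:** state the between-arm test for each of the three DASS-21 scales. Apply Holm across the three and report adjusted beside raw p-values. On the printed values these are 0.036 (depression), 0.036 (stress) and 0.172 (anxiety); recompute them if the between-arm test changes. State that the adjustment was added after the results were known.
- **Abstract and section 5.5:** keep the depression and stress claims and give the adjusted p-values.
- **Discussion of MBT as a nursing intervention, sections 5.3 and 5.10:** bring the anxiety statements into line with the non-significant between-group result in Table 4, and do not present a change pooled over both arms as an intervention effect.
- **Section 3.7, and the power remark in section 5.3:** say only that the sizing used STAI anxiety change over time in the intervention group and gives no planned power for a between-arm DASS-21 comparison on any outcome. Do not write that anxiety was the outcome sized for and was not significant.

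Cost: a few sentences and one extra column in Table 4. No new data are needed. The downside is slightly less favourable p-values for depression and stress.

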#### 3.13.2 Independent Variable:

The independent variable was mentioned as socio-demographics and other information in **Annexure-I**. It included (1) Sectioned (A), Personal information focusing Child Age, Child gender, Primary Care taker area of residence, (2) Section (B), Socioeconomic and educational status of Childs caretaker focusing Occupation, Level of education, Employment status, Income per month and Treatment Expenses. (3) Section C, Cancer Information focusing Diagnoses, Type of cancer, Stage of cancer, treatment being sought, Duration of Chemotherapy, Date of diagnoses, Duration of diagnoses, Family History of cancer and Number of cancer patients in the family of the patient other than this case. (4) Section (D), Pain scale focusing Pain felt by the child at that moment and (5) Section (E), General information related to Anxiety and depression focusing, Caregivers awareness of whether he or she was anxious and depressed? Did caregivers taken any treatment sought for his anxiety and depression? Whether any health professional advices the Caregivers? and Do caregiver had smoking habits?

#### **CHAPTER 4: RESULT**

#### 4.1 Participant flow:

Consolidated Standards of Reporting Trials (COSORT) guidelines were used for organization of methods and results of the study [68]. Total 113 children were admitted in Department of Pediatric Oncology at Indus hospital, Karachi from September 2018 to November 2018. Out of 113, 13 parents along with their children were excluded for not meeting inclusion criteria i.e. non-confirmation of cancer diagnosis, no need for Chemotherapy and refused to participate in study. Thus, 100 parents were randomly allocated to intervention group and Control group with equal number of allocations in each group respectively.

Out of 50 parents in intervention group 4.5% (n=9) were lost during follow up, due to death (n=2) of the children and no response (n =7) from parents. In intervention group 4 children were lost in 1st week, 2 were lost in 2nd week, 2 were lost in 3rd week and 1 was lost in 4th week of follow up. On the other hand, 50 parents along with their children who were randomly allocated to control group as routine care, 3 children died, and 11 participants did not respond afterward. Total 6 were lost in 1st week, 4 were lost in 2nd week, 2 were lost in 3rd week and 2 were lost in 4th week of follow up in control group. It was further identified that lost to follow-up due to death and non-response was somewhat more in control groups as compared to intervention group. The detail is mentioned in *Figure 1* 

